- 774 18. Cognitive Emotions Regulation Questionnaire-short form (CERQ). The CERQ-short form (Garnefski & Kraaij, 2006) is an 18-item questionnaire that produces 9 subscales based on the original 36-item questionnaire. The CERQ self-report 775 776 assesses cognitive coping strategies people tend to use, or what someone thinks, after having experienced threatening or 777 stressful events. Item are rated on a 5-point Likert scale from 1 (almost never) to 5 (almost always) and produce nine 778 subscale scores including: 1) Self-Blame, 2) Blaming Others, 3) Rumination, 4) Catastrophizing, 5) Positive Refocusing, 779 6) Planning, 7) Positive Reappraisal, 8) Putting into Perspective, and 9) Acceptance. The higher the subscale score, the 780 more a specific cognitive strategy is used. The CERQ has good internal consistency and convergent validity across 781 subscales. This measure will be administered at the baseline assessment and the one-month follow-up assessment.
- 19. History of Head Injuries (HHI). The HHI (Schwab et al., 2006) is a modified version of the Defense and Veterans Brain
 Injury Center (DVBIC) 3-Item Screening Tool. Item 1 assesses if an individual has a history of head injury, the count of
 head injuries, and what caused the head injury. Item 2 assess post concussive symptoms that were sustained at the time
 of the worst event. Item 3 assess if the individual is currently experiencing post concussive symptoms. The HHI is positive
 when the participant endorses a history of head injury (question 1) and altered consciousness (question 2, items A-E)
 from the worst head injury sustained. The form was modified for this study for civilian and military samples (i.e.,

Title: Safety, feasibility, and benefits of transcranial direct current stimulation (tDCS) in human subjects with PTSD receiving an exposure-based, behavioral therapy

- deployment and non-deployment related head injuries were collapsed). The HHI has been identified as a gold standard
 for the diagnosis of TBI and has good concurrent validity. The HHI will be administered at baseline assessment.
- 20. Neurobehavioral Symptom Inventory (NSI). The NSI (Cicerone & Kalmar, 1995) is a 22-item measure of behavioral, emotional, and cognitive post concussion symptoms related to a traumatic brain injury. Participants rate the degree they are impacted by each symptom on a 5-point Likert scale from 0 (None-rarely if present) to 4 (Very severe-almost always present and I have been unable to perform at work, school, or home due to this problem. I probably cannot function without help). The NSI total score is a summed score of the items (0 88 range), with greater scores indicating greater impact. The NSI has demonstrated good psychometric properties (King et al., 2012). The NSI will be administered at baseline assessment and one-month follow-up assessment.
- 800
 21. Numeric Rating Scale for Pain Intensity (NRSPI). The NRSPI consists of three separate items that assess current pain, 801 pain at its worst, and pain at its best. Each Item responses range from 0-10 with higher scores suggestive of greater pain 802 severity. There is no total score calculated for this measure. The NRSPI will be administered at baseline assessment and 803 one-month follow-up assessment.
- 22. Patient Reported Outcome Measurement Information System Pain Interference Short Form 8a (PROMIS). The PROMIS (Amtmann et al., 2010) measures the self-reported consequences of pain on relevant aspects of a person's life and may include the extent to which pain hinders engagement with social, cognitive, emotional, physical, and recreational activities. All items assess pain interference over the past seven days on a Likert scale from 0 (Not at all) to 5 (Very Much). The final score is represented by a T-score, a standardized score with a mean of 50 and a standard deviation (SD) of 10.The PROMIS has demonstrated good psychometric properties. Th PROMIS will be administered at baseline assessment and one-month follow-up assessment.
- 23. Credibility/ Expectancy Questionnaire (CEQ) for WET. The CEQ (Devilly & Borkovec, 2000) is a 6-item measure that was 813 designed to assess treatment expectancy and rationale credibility for use in clinical outcomes studies. This measure has 814 been utilized across a number of STRONG STAR treatment trials and can be easily adapted to assess the target 815 intervention(s). For the current proposed study, the CEQ will be adapted to assess the credibility and expectancy for tDCS 816 and WET. These constructs will be assessed separately using two measures specific to each construct. The 6-item CEQ 817 818 assesses both whether the person cognitively understands how the therapy works (credibility) as well as whether the 819 person affectively believes that the therapy will work for them personally (expectancy). The 6-item CEQ has been tested in 217 individuals including 68 male Vietnam veterans and 58 female spouses, 69 individuals diagnosed with general 820 821 anxiety disorder who had received treatment, and 22 individuals who had received either Cognitive Based Therapy (CBT) 822 or Eye Movement Desensitization and Reprocessing (EMDR) for the treatment of PTSD. The scale demonstrated high 823 internal consistency (alpha coefficients ranged from 0.84 to 0.85). Test-retest reliability over a one-week period was found 824 to be 0.82 for expectancy and 0.75 for credibility. The CEQ was able to differentiate between two treatment rationales in 825 one study, one with and one without an encompassing theory while maintaining equivalence between three rationales in another study. Responses to four questions are scored using a 9-point Likert scale (1= not at all, 9= extremely). 826 Responses to two of the questions are scored using an 11-point Likert Scale (0% to 100%). The combined responses are 827 used to generate a score for credibility and another score for expectancy. This measure will be administered prior to the 828 829 second session.
- 24. Credibility/ Expectancy Questionnaire (CEQ) for tDCS. The CEQ (Devilly & Borkovec, 2000) is a 6-item measure that was 831 designed to assess treatment expectancy and rationale credibility for use in clinical outcomes studies. This measure has 832 been utilized across a number of STRONG STAR treatment trials and can be easily adapted to assess the target 833 intervention(s). For the current proposed study, the CEQ will be adapted to assess the credibility and expectancy for tDCS 834 and WET. These constructs will be assessed separately using two measures specific to each construct. The 6-item CEQ 835 assesses both whether the person cognitively understands how the therapy works (credibility) as well as whether the 836 person affectively believes that the therapy will work for them personally (expectancy). The 6-item CEQ has been tested 837 838 in 217 individuals including 68 male Vietnam veterans and 58 female spouses, 69 individuals diagnosed with general 839 anxiety disorder who had received treatment, and 22 individuals who had received either Cognitive Based Therapy (CBT) or Eve Movement Desensitization and Reprocessing (EMDR) for the treatment of PTSD. The scale demonstrated high 840 internal consistency (alpha coefficients ranged from 0.84 to 0.85). Test-retest reliability over a one-week period was found 841 to be 0.82 for expectancy and 0.75 for credibility. The CEQ was able to differentiate between two treatment rationales in 842 one study, one with and one without an encompassing theory while maintaining equivalence between three rationales in 843 another study. Responses to four questions are scored using a 9-point Likert scale (1= not at all, 9= extremely). 844

848

862

Title: Safety, feasibility, and benefits of transcranial direct current stimulation (tDCS) in human subjects with PTSD receiving an exposure-based, behavioral therapy

- Responses to two of the questions are scored using an 11-point Likert Scale (0% to 100%). The combined responses are used to generate a score for credibility and another score for expectancy. This measure will be administered prior to the second session.
- 849 14.3 Physiological/Biospecimen Measures:
- 850
 25. Heart Rate. Heart rate will be assessed using a wearable Fitbit wrist watch device. Heart rate data can be beneficial for individuals who report subjectively being more aroused during the exposure or behaviorally appear to be more activated. Heart rate was selected because it is a robust physiological factor associated with PTSD and stress that can be measured affordably and without specialized expertise. Heart rate will be assessed continuously during the written exposure portion of sessions 1, 3, and 5.
- 855
 26. Galvanic Skin Response. GSR will be assessed using a wearable Fitbit wrist watch device. GSR data can also be
 beneficial for individuals who report subjectively being more aroused during the exposure or behaviorally appear to be
 more activated. GSR was selected because it is a robust physiological factor associated with PTSD and stress that
 can be measured affordably and without specialized expertise. GSR will be tracked using a wearable device to assess
 the pre, post, and peak arousal levels during session. GSR will be assessed continuously during the written exposure
 portion of sessions 1, 3, and 5.
- 27. hCG Pregnancy Test. Pregnancy will be assessed at the baseline appointment using a human chorionic gonadotropin
 (hCG), CLIA-waived pregnancy test. hCG pregnancy tests are a reliable and valid measure of pregnancy that
 evaluates hCG levels in the blood or urine and can determine whether a person is pregnant, as well as whether their
 body is producing the right level of pregnancy hormones.

867 868 869 15.0 REFERENCES.

- Ahmadizadeh, M. J., Rezaei, M., & Fitzgerald, P. B. (2019). Transcranial direct current stimulation (tDCS) for post traumatic stress disorder (PTSD): A randomized, double-blinded, controlled trial. *Brain Research Bulletin*, *153*, 273–
 278. https://doi.org/10.1016/j.brainresbull.2019.09.011
- Amtmann DA, Cook KF, Jensen MP, Chen W-H, Choi SW, Revicki D, Cella D, Rothrock N, Keefe F, Callahan L, Lai J-S
 (2010). Development of a PROMIS item bank to measure pain interference. *Pain 150*(1):173-82.
 functioning in returning veterans. *Journal of Anxiety Disorders*, *28*(3), 310–317.
 https://doi.org/10.1016/i.janxdis.2014.01.005
- Benjet, C., Bromet, E., Karam, E. G., Kessler, R. C., McLaughlin, K. A., Ruscio, A. M., Shahly, V., Stein, D. J., Petukhova,

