- Next, the study team member will place the HR and GSR device on the individual's non-writing hand and begin 306 monitoring. The participant will then begin the writing exposure and tDCS device will be activated. The Soterix 307 device has standardized programming so that all participants receive the same dose (or sham) and intervention 308 based on the set procedures. The tDCS device will be set at 2.0mA for a total of 30-minutes. Once the "start" 309 button is clicked by the study team member, the device is programmed to gradually ramp up current to the set 310 intensity dose (2.0mA in this study) in the first 30-seconds. As seen in Figure 1, in the active intervention the 311 current will remain at 2.0mA for 30-minutes and then the programmed device will gradually ramp down from 312 2.0mA to 0.0mA in the final 30-seconds. 313

Figure 1. tDCS active condition

As seen in Figure 2, during sham stimulation, participants will experience the gradual current ramp up from 0.0 mA to 2.0mA in the first 30-seconds and then a gradual ramp down from 2.0mA to 0.0mA (30-seconds). The programmed device will automatically repeat this process at the end of the set duration of 30 minutes.

319 Figure 2. tDCS sham condition

320

325

314

315

316

317

318

A study team member will be in the immediate proximity during tDCS (or sham)/written exposure to monitor participant safety and abort the tDCS, if necessary. Clicking the "abort" button will initiate a ramp down of current to 0.0mA. A medical provider will also be available should the participant experience a serious AE or require a higher level of medical care.

56GTSPH3C08UU94FUFQ8ULIG00.docx STRONG STAR Template Version 01/31/22

Title: Safety, feasibility, and benefits of transcranial direct current stimulation (tDCS) in human subjects with PTSD receiving an exposure-based, behavioral therapy

• Following the tDCS (or sham) and writing, a study team member will remove the tDCS and HR/GSR device. Consistent with WET, the participant will meet with a study therapist to review their writing for 15-30 minutes. During this time, the participant will also be monitored for safety prior to leaving the appointment.

7.3.1 Collection of Human Biological Specimens. Females will complete a CLIA-waived hCG pregnancy test at baseline for
 screening eligibility purposes.

332

326

327 328

329

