391 Power Analyses: This pilot study is not powered for formal efficacy or mechanistic hypotheses testing. Consistent with 392 research regarding the purpose of a pilot study, our main interests were to evaluate the feasibility of the proposed recruitment, 393 assessment, and treatment protocols, examine safety, and to explore a detectable effect of tDCS across outcomes in 394 preparation for a larger trial (Kraemer et al., 2006; Leon et al., 2011). Although the statistical power of this study is limited, we 395 will perform statistical analyses appropriate for an adequately powered study to identify data analysis issues germane to 396 future planning.

Data Analyses: Prior to developing statistical models, all variable distributions will be examined using frequency distributions,
 scatter plots, and histograms. Statistics such as means or proportions, standard errors, ranges, and estimates of skewness
 and kurtosis will be computed and used as guidelines in the application of analyses. Data transformation procedures may be
 applied to variables with considerable departure from normality.

402

The objectives of this study are to evaluate the safety, feasibility, and PTSD symptom reductions associated with tDCS vs. sham. All statistical analyses will be intent to treat and include all participants randomized at baseline regardless of the statistical analyses will be intent to treat and include all participants randomized at baseline regardless of the

Title: Safety, feasibility, and benefits of transcranial direct current stimulation (tDCS) in human subjects with PTSD receiving an exposure-based, behavioral therapy

extent of study participation. Given the small sample size, we will use a Benjamini-Hochberg Adjustment procedure to mitigate the false discovery rate (two tailed initial p = .05). Analyses will be done SPSS 27 statistical software. As needed, we also have access to SAS 9.4, Stata 14.2, R, and Mplus 8.4 software.

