418 Generalized Linear Mixed Models (GLMM) to Address Aim 3: GLMM will be used to evaluate changes in continuous outcomes associated with tDCS vs. sham. GLMMs are a powerful and flexible statistical extension of linear mixed models 419 420 that can examine outcome variables from different distributions, such as normal (continuous) and binary outcomes. Advantages of likelihood-based regression models over conventional ANOVA include the ability to use data from all 421 participants even if they have only baseline data, relaxation of the assumption of equal variances before and after 422 423 treatment, specification of data distributions other than normal such as Poisson or log-normal, and the ability to analyze 424 longitudinal data in the presence of missing data given the assumption that data are missing at random. GLMM's will 425 include fixed effects of time, treatment (tDCS vs. sham), and the time by treatment interaction. Models will include a priori planned contrasts of mean differences over time and simple effects to evaluate treatment differences at each time point. 426 To inform future studies, we will calculate conventional effect sizes with 95% confidence interval limits (Hertzog, 2008). 427 Hedges' q will be used to calculate continuous outcome effect sizes (e.g., PCL-5). Hedges' q has been recommended 428 over Cohen's d for small samples based on sample size adjustments, yet can be interpreted using the same conventional 429 recommendations as Cohen's d, .20 =small, .50=medium, and .80=large effect sizes (Lakens, 2013). 430 431

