Assessment timepoints are presented in the 7.3 Table. The PCL-5 will be the primary outcome to evaluate changes in 432 PTSD severity from baseline assessment to one-month follow-up, with data points collected during treatment also 433 included in models (Aim 3a). Heart rate monitoring and GSR will be used to evaluate physiological stress arousal during 434 435 the writing exposure task (Aim 3b). Both physiological outcomes will be collected during the writing exposure portion of sessions 1, 3, and 5 to provide before, after, and peak estimates of physiological arousal. Time points of interest for 436 437 physiological outcomes will be the immediate, long-term, and peak effects of tDCS. The immediate effect of tDCS will be 438 defined as changes immediately prior to and after the first written exposure (i.e., change from T_1 to T_2), the third written 439 exposure (change from T_3 to T_4), and the last time participants engage in writing exposure (change from T_5 to T_6). The 440 long-term effect of tDCS will be defined as changes in physiological levels across sessions (session 1 to session 5) prior 441 to engaging in the writing exposure (change from T_1 to T_5) and after the writing exposure (change from T_2 to T_6). The *peak* effect will evaluate change score differences (interaction effect) in the greatest estimate during session 1 to session 5. 442

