- 643 Health Questionnaire tDCS Addendum. The Health Questionnaire tDCS Addendum is an adapted extension of the Health 644 3. Questionnaire and includes items relevant to the assessment of tDCS health contraindications. Items will assess for 645 history of seizures, significant intracranial pathology (e.g., severe traumatic brain injury), major neurological conditions 646 (e.g., Dementia), metallic objects in the body, skin conditions where electrodes are applied that could be exacerbated 647 (e.g., eczema), and adverse reaction to brain stimulation. This measure will be administered at the baseline assessment. 648
- Self-Injurious Thoughts and Behaviors Interview (SITBI). The SITBI (Nock et al., 2007) is a structured interview assessing 650 4. the presence, frequency, and characteristics of self-injurious and suicidal thoughts and behaviors. The SITBI will be 651 administered by an Independent Evaluator, who will instruct the participants to answer the questions based on their entire 652 653 lifetime of experience. The SITBI has shown high interrater reliability, test-retest reliability, and concurrent validity. This 654 measure will be administered at the baseline assessment and the one-month follow-up assessment.

14.2 Self-Report Questionnaires:

649

655

- 656 PTSD CheckList-5 (PCL-5). The PCL-5 (Weathers, Litz, et al., 2013) is a 20-item self-report measure update of the PCL 657 5. designed to assess PSTSD symptoms as defined by the DSM-5. The PCL-5 is currently available and has been shown to 658 have good psychometric properties. The PCL-5 evaluates how much participants have been bothered by PTSD 659 symptoms in the past week (for all assessments during treatment) or the past two weeks (all other assessment time 660 points) as a result of a specific life event. Each item of the PCL-5 is scored on a five-point scale ranging from 0 "not at all") 661 to 4 ("extremely). This measure will be administered at the baseline assessment, prior to each therapy session, and the 662 one-month follow-up assessment. 663

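### Does Benjamini-Hochberg without a listed family, in a plan that also tests arm differences before any stimulation, undermine the Aim 3 results?

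*Combined protocol and SAP*

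**What the plan says.** All of this is in section 7.4.3 unless another section is named.

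- **Adjustment.** "we will use a Benjamini-Hochberg Adjustment procedure to mitigate the false discovery rate (two tailed initial p = .05"). The family is not listed, and the text does not say whether the procedure runs per outcome, per aim or across all tests.
- **Model.** The mixed models "include fixed effects of time, treatment (tDCS vs. sham), and the time by treatment interaction". The planned comparisons are "contrasts of mean differences over time and simple effects to evaluate treatment differences at each time point".
- **PCL-5.** It is the primary outcome for change in "PTSD severity from baseline assessment to one-month follow-up, with data points collected during treatment also" entering the models. On timing, section 14.2 says "This measure will be administered at the baseline assessment, prior to each therapy session, and the" one-month follow-up.
- **HR and GSR.** The immediate effect is "defined as changes immediately prior to and after the first written exposure (i.e., change from T_1 to T_2"), and likewise for sessions 3 and 5. Two long-term contrasts and one peak contrast are added for each outcome.
- **Start of stimulation.** Section 7.3 places the sensor on the hand first, and then: "The participant will then begin the writing exposure and tDCS device will be activated".
- **Estimation.** "we will calculate conventional effect sizes with 95% confidence interval limits", using Hedges' g, to inform later studies.

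The power paragraph disclaims formal efficacy testing, and section 3 describes Aim 3 as exploratory.

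**The concern.** Benjamini-Hochberg gives no answer until its family is fixed. An adjusted p-value depends on how many tests are in the list and on how small the others are. The planned tests differ in kind. Some compare arms after stimulation, some compare arms before it and so cannot show a tDCS effect, and some may be changes over time that the writing therapy should produce in both arms. Adding null tests dilutes a real signal. Adding therapy gains, which are almost sure to be significant, loosens the threshold for everything else. If the list were chosen after unblinding, the same data could support or fail to support a claim for tDCS.

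**Working it through.** **Sample size.** Section 7.4.1 reproduces: 50 × 0.80 = 40 randomized, and 40 × 0.85 = 34 completers. The allocation ratio is not stated; 20 per arm is assumed below.

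**Counting the tests.**
- Arm comparisons at single time points: PCL-5 has 7 (baseline, five sessions, one month) and HR and GSR have 6 each (T1 to T6), so 7 + 6 + 6 = 19.
- Before any stimulation: PCL-5 baseline and session 1, HR T1 and GSR T1, so 2 + 1 + 1 = 4. If T1 is read as falling during writing, which other wording in sections 7.4.3 and 14.3 allows, only the 2 PCL-5 points remain.
- A fifth, the PCL-5 change from baseline to session 1, exists only if contrasts over time are taken to cover every later visit. The plan does not name it.
- On that broad reading there are 3 interactions + 19 simple effects + 18 changes (6 per outcome) = 40 tDCS-sham tests. Removing the five leaves 35.

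**Can the verdict depend on the list?** Yes. When one p-value is small and the rest are large, the adjusted value is m × p.
- p = .003 among the 15 post-stimulation simple effects: 15 × .003 = .045. Among all 19: 19 × .003 = .057.
- It can go the other way. p = .03 beside .4 and .6 gives 3 × .03 = .09. Add chance pre-stimulation values of .002, .004, .01 and .02 and it ranks fifth of seven: 7 × .03 / 5 = .042.

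**How often does it?** Simulation with 20,000 trials per setting. Assumptions not in the documents: correlation .5 within an outcome, independent outcomes, complete cases, therapy gain of 1.2 SD on PCL-5, tDCS effect d growing linearly from session 2 to one month, HR and GSR null. The entries are the percentage of trials in which the PCL-5 baseline-to-one-month verdict differs between readings.

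| Readings compared | d = 0 | d = 0.5 | d = 0.8 |
|---|---|---|---|
| 40 tests v 35 (pre-stimulation tests dropped) | 0.02–0.03 | 0.6–0.7 | 1.9 |
| PCL-5 only, 14 v 11 | 0.1 | 2.3 | 4.2 |
| Three readings of tDCS-sham tests only (13; 40; per outcome) | – | 6.6 | 16.8 |
| Five readings, two of them including within-arm changes | 1 | 14 | 28 |

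Halving the therapy gain lowers the last row to about 10% and 23%. The pre-stimulation tests account for very little. Much of the rest comes from two readings that mix within-arm therapy gains with tDCS tests.

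**Is the promised error rate kept?** The plan promises control of the false discovery rate.
- In the 72-test family (40 plus 32 within-arm changes), with no tDCS effect, the chance of any false tDCS claim is about 13%, but the false discovery rate is about 4%, below the nominal 5%.
- Running the procedure separately for three outcomes gives about 13% for any false claim, close to 1 − .95³ = 14%. That is the familywise rate of three families each controlled at 5%, not a failure of the method.

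**What would a fixed list gain?** With the PCL-5 contrast inside a 35-test list, its power is 6% at d = 0.5 and 29% at d = 0.8. On its own it is 34% and 69%. Leaving it outside raises the chance of any false tDCS claim from 4–5% to about 9%. Each choice has a cost, and nothing in the plan's aims settles which to prefer.

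**The case for a change.** The strongest case for acting is that the sponsor chose to adjust, said the analyses would suit an adequately powered study so as to expose analysis problems, and then left the adjustment undefined. Plausible readings disagree on the main PCL-5 verdict in 14% to 28% of trials at medium to large effects. If someone picked the family after seeing the results, the chance of a false tDCS claim would be about 22%. A paragraph would close the gap at almost no cost.

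Part of this stands. The family is not written down, and the pre-stimulation comparisons say nothing about tDCS. It is also true that controlling the false discovery rate over a pooled family does not control it for the tDCS-sham tests alone, so the 13% in the 72-test reading would matter to someone who looked only at those tests. But that reading requires pooling therapy gains with arm comparisons, which few analysts would do when the question is tDCS against sham. Its size also depends on the assumed gain: at half the gain the figure is 5%. The 22% presumes selective choice after unblinding, which nothing in the plan proposes. The 28% needs a 0.8 SD effect and all five readings treated as live options.

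**Conclusion.** The gap is missing detail, not an error, and no change to the plan follows. An analyst who sets the family before unblinding, takes the post-stimulation tDCS-sham contrasts as that family and describes the rest has ample guidance: PCL-5 from baseline to one month is already named for Aim 3a, and the HR and GSR contrasts are spelled out. The pre-stimulation tests alter the PCL-5 one-month verdict in under 2% of simulated trials, or up to about 4% in a PCL-5-only family. Control of the false discovery rate holds at about 4% in the pooled 72-test reading with no tDCS effect. Aims 1 and 2 are descriptive, so the adjustment does not touch them. Hedges' g and its 95% interval, which a later trial would use, are the same whatever the family. These sizes rest on the assumed correlation, therapy gain, effect shape, equal allocation and complete data. They would move with those inputs, but the effect sizes and intervals would remain independent of the family chosen.
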